## 24 SPONSOR AUDITS AND INSPECTIONS BY REGULATORY AGENCIES

For the purpose of ensuring compliance with the Clinical Trial Protocol, Good Clinical Practice and applicable regulatory requirements, the Investigator should permit auditing by or on the behalf of the Sponsor and inspection by applicable regulatory authorities.

The Investigator agrees to allow the auditors/inspectors to have direct access to his/her study records for review, being understood that this personnel is bound by professional secrecy, and as such will not disclose any personal identity or personal medical information.

The Investigator will make every effort to help with the performance of the audits and inspections, giving access to all necessary facilities, data, and documents. As soon as the Investigator is notified of a future inspection by the authorities, he will inform the Sponsor and authorize the Sponsor to participate in this inspection.

The confidentiality of the data verified and the protection of the patients should be respected during these inspections.

Any result and information arising from the inspections by the regulatory authorities will be immediately communicated by the Investigator to the Sponsor.

The Investigator shall take appropriate measures required by the Sponsor to take corrective actions for all problems found during the audit or inspections.

# 25 PREMATURE DISCONTINUATION OF THE STUDY OR PREMATURE CLOSE-OUT OF A SITE

## 25.1 Decided by the Sponsor in the Following Cases:

- 1. In the event the results of the Clinical Trial do not appear to be scientifically convincing to the Sponsor;
- 2. If the aim of the Clinical Trial has become outdated or is no longer of interest;
- 3. If the information on the product leads to doubt as to the benefit/risk ratio;
- 4. If the Investigator has received from the Sponsor all Investigational Product, means and information necessary to perform the Clinical Trial and has not included any patient after a reasonable period of time mutually agreed upon;
- 5. In the event of breach by the Investigator of a fundamental obligation under this agreement, including but not limited to breach of the Clinical Trial Protocol, breach of the applicable laws and regulations or breach of the ICH guidelines for GCP;
- 6. If the total number of patients are included earlier than expected; In any case the Sponsor will notify the Investigator of its decision by written notice.

# 25.2 Decided by the Investigator

The Investigator must notify (30 days' prior notice) the Sponsor of his/her decision and give the reason in writing. In all cases (decided by the sponsor or by the Investigator), the appropriate Ethics Committee(s) (IRB/EC) and Health Authorities should be informed.

## 26 CLINICAL TRIAL PROTOCOL AMENDMENTS

Any protocol amendments will be added as stand-alone documents. In addition, any and all revisions dictated by the amendments will be made in the protocol. Each time a protocol is amended, a new amended version date will be added to the cover page.

All appendices attached hereto and referred to herein are made part of this Clinical Trial Protocol. The Investigator should not implement any deviation from, or changes of the Clinical Trial Protocol without agreement by the sponsor and prior review and documented approval/favorable opinion from the IRB/EC of an amendment, except where necessary to eliminate an immediate hazard(s) to clinical trial patients, or when the change(s) involves only logistical or administrative aspects of the trial. Any change agreed upon will be recorded in

writing, the written amendment will be signed by the Investigator and by the Sponsor and the signed amendment will be filed with this Clinical Trial Protocol. Any amendment to the Clinical Trial Protocol requires written approval/favorable opinion by the IRB/EC prior to its implementation, unless there are overriding safety reasons. In some instances, an amendment may require a change to the Informed Consent Form. The Investigator must receive an IRB/EC approval/favorable opinion concerning the revised Informed Consent Form prior to implementation of the change.

# 27 APPENDIX A-SCHEDULE OF EVENTS

Visit name (Day)	Screening	Baseline (Beginning of 4 week baseline period)	Randomization (End of 4 week baseline period)	Prevention Treatment Week 4	Prevention Treatment Week 8	Prevention Treatment Week 12	Follow-Up (End of Study) Week 16	Unanticipated/Early Termination Visit
Visit	V1 (Day -29)	V2 (Day -28)	V3 (Day 0)	V4 (Day 28)	V5 (Day 56)	V6 (Day 84)	V7 (Day 112)	
Visit Window, in Days	-42 to -28	-31 to -27	±3	±3	±3	±3	±3	
Informed Consent 	X							
Inclusion/Exclusion Criteria 		X	$X^{17}$					
Demographics								
Medical history								
Smoking status								
Concomitant medications		X	X	X	X	X	X	
Vital signs (HR, BP, respiratory rate)	X		X	X	X	X	X	
Brief Physical exam	X	X	X	X	X	X	X	

Neurological exam	X	X	X	X	X	X	X	X
Body weight	X	X	X	X	X	X	X	
Height	X							
Blood collection 			X	X	X	X	X	X
12-lead ECG	X		X			X		
Randomization 			X					
Nasal inspection 	X	X	X	X	X	X	X	X
Delivery of Investigational Product			X					
Investigational Product application 			X	X	X	X		
Investigational Product compliance 			X	X	X	X		X
Counseling 			X	X	X			X
Laboratory testing 	X		X			X		X
Urinary pregnancy test 	X							
Nasal fluid 			X	X	X	X	X	X
Safety AEs	X	X	X	X	X	X	X	X

## CONFIDENTIAL

Study diary 	X	X	X	X	X	X	X	X
Migraine pain intensity score	X	X	X	X	X	X	X	X
MIDAS 		X	X			X		X
HIT-6 		X	X	X	X	X	X	X
MSQL 		X	X	X	X	X	X	X
CGI 		X	X	X	X	X	X	X
Subject Satisfaction Survey							X	X 

- 1. Informed consent can be obtained up to 14 days prior to the baseline visit (V2).
- 2. Inclusion and exclusion criteria will be reviewed at Screening (V1), Baseline (V2), and Randomization (V3) visits to make sure nothing changed.
- 3. Blood samples for biomarkers will be collected and processed on site. Serum/plasma samples will be frozen onsite and shipped to the Central lab for storage.
- 4. Subject's demographic data and medical history are blinded to the statistician for randomization and treatment assignment. Only subjects with 4-14 migraine headache days per month during baseline period (28 days between V2 and V3) will be randomized.
- 5. Nasal inspection will include clinical examination of the nasal mucosa, sinuses, and upper airway using an otoscope.
- 6. Subjects will be trained for in-home treatment/assessment on the use of the nasal spray, and have their first dose of treatment on site (V3). Subjects will remain onsite for observation for 1 hour post dosing. Subjects will then be dispensed study medication for 12 weeks of at home dosing.
- 7. Weight of individual IP bottles will be obtained at visits V3 (before and after first dose), V4, V5, V6, and unanticipated/early termination visit.
- 8. Subjects will be counseled on the application of the nasal spray, study diary, and answer any questions.
- 9. Fasting blood sample for a comprehensive metabolic panel, complete blood count, chemistry, lipid panel, and liver function test-15 ml. Also includes urinalysis. Patients should fast for at least 8 hours before the test. Blood will be shipped to the central lab for processing.
- 10. Urine pregnancy test to be done on WOCBP.
- 11. Intranasal strip will be used to collect nasal fluid for inflammatory cytokines. Optionally, nasal fluid may be evaluated for nasal microbiome (e.g., PCR) to confirm presence of B244.
- 12. Subjects will be asked to fill out a daily migraine-history diary from screening to treatment with study drug and a migraine-treatment diary from treatment through the remainder of the follow-up period. Baseline period, prevention treatment, and follow up observation period for study assessments will be daily and will include dosing, migraine days, headache days, migraine intensity, headache intensity, rescue meds (acute migraine specific meds), nausea, vomiting, photophobia, and sonophobia. Collect sufficient information about the headache in the trial (i.e., headache intensity, presence/absence of associated symptoms, unilateral/bilateral location, aggravation by exercise, throbbing/non-throbbing) to verify the headache is a migraine.
- 13. Migraine Disability Assessment questionnaire.
- 14. Headache Impact Test-6 questionnaire.
- 15. Migraine Specific Quality of Life questionnaire.
- 16. Clinical Global Impression scale
- 17. Subjects are randomized upon confirming the inclusion/exclusion criteria and the entry criteria of 4-14 migraine headache days during the baseline period.
- 18. Only for Early Termination Visit due to study discontinuation or withdrawal.

# 28 APPENDIX B- MIGRAINE DISABILITY ASSESSMENT (MIDAS) QUESTIONNAIRE

#### The Migraine Disability Assessment Test

The **MIDAS** (Migraine Disability Assessment) questionnaire was put together to help you measure the impact your headaches have on your life. The information on this questionnaire is also helpful for your primary care provider to determine the level of pain and disability caused by your headaches and to find the best treatment for you.

#### **INSTRUCTIONS**

Please answer the following questions about ALL of the headaches you have had over the last 3 months. Select your answer in the box next to each question. Select zero if you did not have the activity in the last 3 months. Please take the completed form to your healthcare professional.

- 1. On how many days in the last 3 months did you miss work or school because of your headaches?
- 2. How many days in the last 3 months was your productivity at work or school reduced by half or more because of your headaches? (Do not include days you counted in question 1 where you missed work or school.)
- 3. On how many days in the last 3 months did you not do household work (such as housework, home repairs and maintenance, shopping, caring for children and relatives) because of your headaches?
- 4. How many days in the last 3 months was your productivity in household work reduced by half of more because of your headaches? (Do not include days you counted in question 3 where you did not do household work.)
- 5. On how many days in the last 3 months did you miss family, social or leisure activities because of your headaches?

Total (Questions 1-5)

### What your Physician will need to know about your headache:

- On how many days in the last 3 months did you have a headache? (If a headache lasted more than 1 day, count each day.)
- On a scale of 0 10, on average how painful were these headaches? (where 0=no pain at all, and 10= pain as bad as it can be.)

**Scoring:** After you have filled out this questionnaire, add the total number of days from questions 1-5 (ignore A and B).

MIDAS Grade	Definition	MIDAS Score
I	Little or No Disability	0-5
II	Mild Disability	6-10
III	Moderate Disability	11-20
IV	Severe Disability	21+

If Your MIDAS Score is 6 or more, please discuss this with your doctor.

# 29 APPENDIX C- HEADACHE IMPACT TEST-6 (HIT-6) QUESTIONNAIRE

=	`		sability) This question eel and what you cannot	· ·
headaches.				
INSTRUCTION	ONS : To com	plete, please circle one	answer for each quest	ion.
1. When you	have headache	s, how often is the pair	n severe?	
Never	Rarely	Sometimes	Very often	Always
	do headaches school, or socia	5	usual daily activities i	ncluding household
Never	Rarely	Sometimes	Very often	Always
3. When you	have a headacl	ne, how often do you w	vish you could lie down	n?
Never	Rarely	Sometimes	Very often	Always
4. In the past your headach		often have you felt too	tired to do work or da	ily activities because of
Never	Rarely	Sometimes	Very often	Always
5. In the past	4 weeks, how	often have you felt fed	up or irritated because	e of your headaches?
Never	Rarely	Sometimes	Very often	Always
6. In the past activities?	4 weeks, how	often did headaches lir	mit your ability to conc	entrate on work or daily
Never	Rarely	Sometimes	Very often	Always
Column 1	Column 2	Column 3	Column 4	Column 5
Column 1 (N	ever): 6 points	each	_	
Column 2 (Ra	arely): 8 points	each		

To score, add points for answers in each of	column.
Column 5 (Always): 13 points each	
Column 4 (Very often): 11 points each	
Column 3 (Sometimes): 10 points each	·

Class I: 36-49, Class II: 50-55, Class III: 56-59, Class IV: 60 and more.

It is suggested to talk to your physician for class II and more.

CONFIDENTIAL

# 30 APPENDIX D- MIGRAINE SPECIFIC QUALITY OF LIFE (MSQL) QUESTIONNAIRE

## MIGRAINE SPECIFIC QUALITY OF LIFE QUESTIONNAIRE (VERSION 2.1)

#### **PATIENT INSTRUCTIONS:**

Please fill out this questionnaire. It will help us understand the effects of migraine headache on your daily activities.

The questionnaire has been designed so that it can be completed quickly and easily. Please check only one answer for each question. You should answer every question.

#### Thank you for your time.

While answering the following questions, please think about *all migraine attacks* you may have had *in the past 4 weeks*.

- In the past 4 weeks, how often have migraines interfered with how well you dealt with family, friends and others who are close to you? (Select only one response.) 1 None of the time 2 A little bit of the time 3 Some of the time 4 A good bit of the time 5 Most of the time 6 All of the time
- In the past 4 weeks, how often have migraines interfered with your leisure time activities, such as reading or exercising? (Select only one response.) 1 None of the time 2 A little bit of the time 3 Some of the time 4 A good bit of the time 5 Most of the time 6 All of the time
- 3. In the past 4 weeks, how often have you had **difficulty** in performing work or daily activities because of migraine symptoms? (Select only **one** response.) 1 None of the time 2 A little bit of the time 3 Some of the time 4 A good bit of the time 5 Most of the time 6 All of the time
- 4. In the past 4 weeks, how often did migraines **keep you** from getting as much done at work or at home? (Select only **one** response.) 1 None of the time 2 A little bit of the time 3 Some of the time 4 A good bit of the time 5 Most of the time 6 All of the time

- 5. In the past 4 weeks, how often did migraines **limit** your ability to concentrate on work or daily activities? (Select only **one** response.) 1 None of the time 2 A little bit of the time 3 Some of the time 4 A good bit of the time 5 Most of the time 6 All of the time
- 6. In the past 4 weeks, how often have migraines **left you too tired** to do work or daily activities? (Select only **one** response.) 1 None of the time 2 A little bit of the time 3 Some of the time 4 A good bit of the time 5 Most of the time 6 All of the time
- 7. In the past 4 weeks, how often have migraines **limited** the number of days you have felt energetic? (Select only **one** response.) 1 None of the time 2 A little bit of the time 3 Some of the time 4 A good bit of the time 5 Most of the time 6 All of the time
- 8. In the past 4 weeks, how often have you had to **cancel** work or daily activities because you had a migraine? (Select only **one** response.) 1 None of the time 2 A little bit of the time 3 Some of the time 4 A good bit of the time 5 Most of the time 6 All of the time
- 9. In the past 4 weeks, how often did you **need help** in handling routine tasks such as every day household chores, doing necessary business, shopping, or caring for others, when you had a migraine? (Select only **one** response.) 1 None of the time 2 A little bit of the time 3 Some of the time 4 A good bit of the time 5 Most of the time 6 All of the time
- 10. In the past 4 weeks, how often did you have to **stop** work or daily activities to deal with migraine symptoms? (Select only **one** response.) 1 None of the time 2 A little bit of the time 3 Some of the time 4 A good bit of the time 5 Most of the time 6 All of the time
- 11. In the past 4 weeks, how often were you **not able to go** to social activities such as parties, dinner with friends, because you had a migraine? (Select only **one** response.)

  1 None of the time 2 A little bit of the time 3 Some of the time 4 A good bit of the time 5 Most of the time 6 All of the time
- 12. In the past 4 weeks, how often have you **felt** fed up or frustrated because of your

migraines? (Select only **one** response.)  $_1$  None of the time  $_2$  A little bit of the time  $_3$  Some of the time  $_4$  A good bit of the time  $_5$  Most of the time  $_6$  All of the time

- 13. In the past 4 weeks, how often have you **felt** like you were a burden on others because of your migraines? (Select only **one** response.) 1 None of the time 2 A little bit of the time 3 Some of the time 4 A good bit of the time 5 Most of the time 6 All of the time
- 14. In the past 4 weeks, how often have you been **afraid** of letting others down because of your migraines? (Select only **one** response.) 1 None of the time 2 A little bit of the time 3 Some of the time 4 A good bit of the time 5 Most of the time 6 All of the time

## 31 APPENDIX E- CLINICAL GLOBAL IMPRESSION (CGI) SCALE

#### **CLINICAL GLOBAL IMPRESSION**

### 1. Severity of illness

Considering your total clinical experience with this particular population, how mentally ill is the patient at this time?

- 0 = Not assessed 1 = Normal, not at all ill 2 = Borderline mentally ill 3 = Mildly ill
- 4 = Moderately ill 5 = Markedly ill 6 = Severely ill 7 = Among the most extremely ill patients
- **2. Global improvement:** Rate total improvement whether or not, in your judgement, it is due entirely to drug treatment. Compared to his condition at admission to the project, how much has he changed?
- 0 = Not assessed 1 = Very much improved 2 = Much improved 3 = Minimally improved
- 4 = No change 5 = Minimally worse 6 = Much worse 7 = Very much worse
- **3. Efficacy index:** Rate this item on the basis of **drug effect only**. Select the terms which best describe the degrees of therapeutic effect and side effects and record the number in the box where the two items intersect. EXAMPLE: Therapeutic effect is rated as 'Moderate' and side effects are judged 'Do not significantly interfere with patient's functioning'.

Therapeutic effect	Side effects				
	None	Do not significantly interfere with patient's functioning	Significantly interferes with patient's functioning	Outweighs therapeutic effect	
Marked Vast improvement. Complete or nearly complete remission of all symptoms	01	02	03	04	
Moderate Decided improvement.	05	06	07	08	

Partial remission of symptoms				
Minimal Slight improvement which doesn't alter status of care of patient	09	10	11	12
Unchanged or worse	13	14	15	16

Not assessed = 00

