## 4.2 Secondary

- Mean change in monthly migraine days from baseline to 12 weeks of treatment.
- Proportion of subjects experiencing a 50%, 75%, and 100% reduction in monthly migraine days from baseline to 12 weeks of treatment.
- Mean change in monthly migraine attacks from baseline to 12 weeks of treatment.
- Mean change in monthly migraine days from baseline to the 4-week period after first dose of study drug.
- Mean change in monthly acute migraine specific medication days from baseline to 12 weeks of treatment.
- Mean change in monthly moderate and severe headache days (migraine pain-intensity score) from baseline to 12 weeks of treatment.
- Mean change in monthly headache days from baseline to 12 weeks of treatment.
- Mean change in monthly headache hours from baseline to 12 weeks of treatment.
- Mean change from baseline to 12 weeks of treatment in disability, as measured by the Migraine Disability Assessment (MIDAS) questionnaire.
- Mean change from baseline to 12 weeks of treatment in monthly Headache Impact Test-6 (HIT-6) questionnaire.

- Mean change from baseline to 12 weeks of treatment in monthly Migraine Specific Quality of Life questionnaire (MSQL) questionnaire.
- Safety assessments after 28 day follow-up period.
- Mean change in baseline Clinical Global Impression (CGI) score to end of treatment period.

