#### 6.4 Exclusion Criteria

Deviations from exclusion criteria are not allowed because they can potentially jeopardize the scientific integrity of the study, regulatory acceptability or participant safety. Therefore, adherence to the criteria as specified in the protocol is essential.

Participants will be excluded from the study if any of the following criteria are met:

- 1. Headache on greater than 14 days/month in any of the three months (90 days) preceding entry into the study.
- 2. Use of acute migraine-specific medications (e.g., ergotamine, triptan) on more than 10 days per month in the previous 3 months and during study.
- 3. Use of intranasal migraine medications during study.
- 4. Use of any intranasally administered over-the-counter product or nasal irrigation (e.g., neti pot) during study.
- 5. Opioids/barbiturates used on more than 4 days per month in the previous 3 months and throughout the duration of the study.
- 6. Use of analgesics (including acetaminophen, nonsteroidal anti-inflammatory drugs [NSAIDs], acetylsalicylic acid, or combination analgesics) for migraine or non-migraine headaches on more than 14 days per month in the previous 3 months and during study.
- 7. Use of migraine prevention medication within two months prior to study and throughout the duration of the study.
- 8. Botulinum toxin injection within 3 months prior to screening or during study.
- 9. Anti-CGRP monoclonal antibody (e.g., erenumab, fremanezumab, galcanezumab, and eptinezumab) injection or infusion within 4 months prior to screening or during study.
- 10. Small molecule anti-CGRP medications in the 30 days prior to the screening visit.
- 11. Use of systemic antibiotics during study.
- 12. Pregnancy or breast-feeding.
- 13. Female of childbearing potential not using adequate contraceptive measures.
- 14. Inability to give informed consent.
- 15. History of neurological, psychiatric, or any other medical condition that in the opinion of the investigator may compromise the subject's ability to safely participate in the study.
- 16. Subjects with any significant clinical abnormalities which may interfere with study participation.
- 17. Prior use of AO+ Mist
- 18. Subjects with immunodeficiencies, nasal lesions, nasal polyps, or sinus infections.
- 19. Subjects who have participated in an investigational drug trial in the 30 days prior to the screening visit.
- 20. Inability to maintain at least 80% diary compliance during the study from baseline to follow-up.

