#### 11.15 CGI

Clinical Global Impression (CGI) scale is an investigator assessment that will be administered at the times indicated in the Schedule of Events Table (Appendix A): Baseline (beginning of 4 week baseline period; V2), Randomization (end of 4 week baseline period; V3), Prevention Treatment Week 4 (V4), Prevention Treatment Week 8 (V5), Prevention Treatment Week 12 (V6), Follow-Up Week 16 (End of Study; V7), and at Unanticipated/Early Termination Visit should one occur. The clinician will assess measures of symptom severity, treatment response and the efficacy of treatments in patients.

CGI scale can be found in Appendix E.

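### The CGI severity item asks how mentally ill the patient is, so the rating behind the CGI change endpoint need not register migraine

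*Protocol*

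**What the plan says.** Section 4.2 of the protocol lists as a secondary endpoint "Mean change in baseline Clinical Global Impression (CGI) score to end of treatment period". The synopsis and section 13 repeat it. Section 14.5 treats the change in CGI score as continuous and compares arm means with a one-sided, equal-variance z-test.

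Section 11.15 describes the CGI as an investigator assessment: "The clinician will assess measures of symptom severity, treatment response and the efficacy of treatments in patients". It then refers to Appendix E for the form.

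Appendix E has three items:

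- **Item 1, severity of illness.** The question is "Considering your total clinical experience with this particular population, how mentally ill is the patient at this time". The rated anchors run "1 = Normal, not at all ill 2 = Borderline mentally ill 3 = Mildly ill" and then "4 = Moderately ill 5 = Markedly ill 6 = Severely ill 7 = Among the most extremely ill patients".
- **Item 2, global improvement.** The question is "Compared to his condition at admission to the project, how much has he changed".
- **Item 3, efficacy index.** A grid code that sets therapeutic effect against side effects.

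Exclusion criterion 15 in section 6.4 begins "History of neurological, psychiatric, or any other medical condition that in the opinion of the investigator may compromise" and leaves the judgement to the investigator.

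**The concern.** The trial enrols people with episodic migraine, yet the item 1 question asks about mental illness. The other questionnaires in the appendices (MIDAS, HIT-6 and MSQL) each name headache or migraine. The CGI form does not, and no text in the protocol adapts it.

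A question that does not point at the disease may not detect an effect on it. A rater who follows the printed words records the subject's mental state; a rater who assumes migraine is meant records something else. If both readings occur, the tested mean combines two constructs and a real difference between arms is pulled towards zero. An analysis plan can choose which item to analyse, but it cannot change what the rater was asked.

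**Working it through.** The protocol gives no figure to reproduce here. The check is a comparison of texts, followed by an illustration of size.

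**1. Do the form and section 11.15 measure the same thing?** Section 11.15 lists symptom severity, treatment response and efficacy of treatment, which line up in order with items 1, 2 and 3. Item 1 should therefore be symptom severity. Its question and its second anchor ask about mental illness instead. Of the seven rated anchors (1 to 7, leaving out the code for not assessed), one carries that wording, anchor 2. Anchors 3 to 7 speak only of being ill. No other part of the protocol changes the question.

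**2. Which item can carry a change from baseline?** Item 2 is already a rating of change since entry. Item 3 rates drug effect and has no meaning before treatment. Item 1 is the only rating of current status that can be taken both before treatment and at Week 12. That item 1 is the endpoint score is an inference, because the protocol never says so.

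**3. What does a literal answer give?** A subject without mental illness scores 1 before treatment and 1 at Week 12, so the change is 1 − 1 = 0 regardless of migraine days. Criterion 15 may remove some psychiatric illness, at the investigator's judgement. That makes low literal scores plausible for many subjects, but it does not exclude all psychiatric illness.

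**4. How large is the effect?** The documents do not say how many raters would read the item literally. Assume a fraction f of subjects, equal in all arms, is rated 1 at both visits, and that the rest have mean change m_A on active treatment and m_V on vehicle. Then

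- mean change in each arm = f × 0 + (1 − f) × m = (1 − f) m
- difference between arms = (1 − f)(m_A − m_V)

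The zeros also shrink the spread. If the remaining subjects have standard deviation s, the variance in an arm is (1 − f)s² + f(1 − f)m². The standardised difference that drives the z-test is then multiplied by about √(1 − f) when m is small relative to s, and by less than that otherwise.

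| f (assumed) | Factor on the raw difference, 1 − f | Factor on the standardised difference, at most √(1 − f) |
|---|---|---|
| 25% | 0.75 | 0.87 |
| 50% | 0.50 | 0.71 |
| 75% | 0.25 | 0.50 |
| 100% | 0 | no difference can appear |

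**5. How much of the trial is touched?** Section 4.2 has 13 secondary bullets. One is a safety assessment, which leaves 13 − 1 = 12 for efficacy, and the CGI is 1 of those 12.

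**The case against.** The strongest reply is that investigators will understand what is meant. Section 11.15 tells them that the first thing assessed is symptom severity. The item is headed as severity of illness, its question refers to the particular population, and five of the seven rated anchors say only ill. Guidance to raters may also sit in sponsor study procedures that are not part of the protocol. This stands as a reason why some ratings will reflect migraine, and why f is unknown and could be small. It does not remove the defect: the endpoint then depends on raters setting aside the printed question, and nothing in the protocol tells them to do so.

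Two narrower points also stand in part. The factor (1 − f) describes the raw mean difference; the loss for the planned z-test can be smaller, as the table shows, but the direction is the same. Naming the scored item and the baseline visit is commonly left to an analysis plan, so their absence is not counted here.

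Finally, the CGI is one supportive endpoint among several that measure migraine or headache directly, and the error cannot by itself create a false claim of efficacy. That is right, and it limits the weight of the point.

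**Conclusion.** The concern holds. As written, the item 1 question and anchor 2 in Appendix E do not fit the purpose stated in section 11.15. Followed literally, the item cannot register a change in migraine for a subject without mental illness.

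The wording defect is certain from the text. The consequence for the endpoint rests on two assumptions: that item 1 is the score analysed, and that some raters answer the question as printed. The size depends on an unknown fraction f and runs from no loss at f = 0 to complete loss at f = 100%, always towards no difference between arms.

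The effect is confined to 1 of 12 secondary efficacy endpoints. The safety primary endpoint, the migraine-day endpoints and the sample size are unaffected, and items 2 and 3 of the CGI carry no such wording. It should be corrected, but it does not threaten the trial's main conclusions.

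**What to change.** Reword the item 1 question and anchor 2 in Appendix E so that they ask about severity of migraine, in line with section 11.15.

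As a minor clarification at the same time, name item 1 as the score for the mean-change endpoint and state one pre-treatment visit as its baseline, since the CGI is taken at both V2 and V3, with V6 as the end of treatment. Keep the synopsis and sections 4.2, 11.15, 13 and 14.5 consistent with this.

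Under section 26 the appendices are part of the protocol, and under section 16.4 changes need IRB approval, so the cost is a protocol and form amendment. No visit or procedure is added. The drawback is that item 1 ratings already taken under the present wording would not be comparable with later ones, which argues for making the change early.
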